2.7.5 Implementation of non-intervention study

The treating physician will receive a documentation folder and instructions from the field staff of Servier. The patient should be informed of his/her participation in this study and the transfer of his/ her clinical data from the site to the responsible professional subcontractor for statistical analyses. Written informed consent must be obtained from the patient at the inclusion visit. The patient will receive a patient information sheet and a signed informed consent form. The second informed consent form must be archived by the doctor. Forms of documents should be filled in a readable form with a ballpoint pen in blue or black. In case of correction of erroneous data, they must be crossed out and replaced with the correct data. Corrections should be verified by the initials and date. No data should be deleted or erased. To ensure a high number of cases suitable for analysis, document forms should always be completed carefully and completely. In case of occurrence of adverse events (AEs), adverse drug reactions (ARDs), or special situations, it is necessary to follow the requirements listed in the section **Ошибка! Источник ссылки не найден. «Responsibilities of the investigator»**. Please hand over the folder with the complete documentation to your Servier local executive.

Patients will undergo clinical assessment and receive the standard medical care as usual determined by the treating doctor based on their clinical judgement and national guidelines. Patients will not receive experimental treatment as a consequence of their participation in the observational study.

3 Pharmacovigilance

Definitions

3.1.1 Pharmacovigilance information

Pharmacovigilance data include any unintended or adverse event associated with the use of a medicinal product in humans, whether or not considered drug related, including the following special situations (situations where no adverse event occurred but information needs to be collected):

- exposure during pregnancy or breastfeeding;
- overdose, abuse, misuse, off-label uses, medication error, or occupational exposure (including professional one);
- lack of treatment effectiveness of a medicinal product;
- any suspected transmission via medicinal product of an infection agent;
- unintended therapeutic benefit.

3.1.2 Adverse Event (AE)

Adverse event is any untoward medical occurrence in a patient or a clinical-trial subject who received the medicinal product, which does not necessarily have a causal relationship with the use of this medicinal product.

An adverse event can therefore be any unfavourable and unintended sign (e.g. an abnormal laboratory finding), symptom, or disease temporally associated with the use of a medicinal product, whether or not considered related to the medicinal product.

3.1.3 Adverse (drug) reaction (ADR)

Adverse reaction (synonyms: Adverse drug reaction, Suspected adverse (drug) reaction, Adverse effect, Undesirable effect) is a response to a medicinal product which is noxious and unintended.

“Response” in this context means that a causal relationship between a medicinal product and an adverse event is at least a reasonable possibility.

Adverse reactions may arise from use of the product within or outside the terms of the marketing authorization or from occupational exposure. Conditions of use outside the marketing authorization include off-label use, overdose, misuse, abuse and medication errors.

3.1.4 Serious adverse (drug) reaction (SADR)

Serious adverse reaction is an adverse reaction, which results in death, is life-threatening, requires in-patient hospitalisation or prolongation of existing hospitalisation, results in persistent or significant disability or incapacity, or is a congenital anomaly/birth defect.

“Life threatening” in this context refers to a reaction in which the patient was at risk of death at the time of the reaction; it does not refer to a reaction that hypothetically might have caused death if more severe.

Medical and scientific judgement should be exercised in deciding whether other situations should be considered serious reactions, such as important medical events that might not be immediately life threatening or result in death or hospitalisation but might jeopardise the patient or might require intervention to prevent one of the other outcomes listed above.

Examples of such events are intensive treatment in an emergency room or at home for allergic bronchospasm, blood dyscrasias or convulsions that do not result in hospitalisation or development of dependency or abuse.

Any suspected transmission via a medicinal product of an infectious agent is also considered a serious adverse reaction.

Responsibilities

3.2.1. Events to be reported

All available information about the following reported events occurring during the study will be recorded:

- All serious adverse drug reactions related to the use of bisoprolol+perindopril SPC;
- All non-serious adverse drug reactions related to the use of SPC bisoprolol+perindopril);
- All reports about special situations (see **Ошибка! Источник ссылки не найден.**);
- All adverse events

3.2.2. Responsibilities of the investigator

At the visits during the study, the doctor clarifies in a patient participating in the study whether he/she had noticed any adverse events (serious or not serious according to the criteria of severity). The investigator should determine the presence/absence of a causal relationship between the use of the study drug and the adverse event, the presence/absence of criteria for severity, and then monitor the outcome of the event. In case of detection of any adverse event/adverse drug reaction or occurrence of a special situation during the study (serious or not serious according to the criteria of severity), the investigator must fill out the «*Adverse event/adverse drug reaction/special situation reporting form*» (Appendix) without waiting for the clinical outcome or the results of additional investigations.

If the event is serious, the form should be sent immediately (same or next working day at the latest) to Servier company in Russia via e-mail to address [contact] or by fax to number [name]. The anonymized copies of all the available and relevant laboratory findings, hospitalisation reports or other investigation results performed in relation to the adverse event should be attached to the form.

3.2.3 Responsibilities of the Sponsor/Marketing Authorisation Holder

Independently of the regulatory obligations of investigator, the sponsor/marketing authorisation holder (MAH) must report the pharmacovigilance data to the appropriate authorities in accordance with the Good Pharmacovigilance Practice and local regulations.

Cases of adverse event are considered to be closed when the patient has recovered or his/her condition was stabilised, providing that the available data are sufficiently detailed for adequate medical analysis of the case.

4 Data management, quality management, statistics and reporting

Data management

Data collection in this study is carried out using documentation forms. Centralized data entry will be carried out by a responsible professional subcontractor for statistical analyses after receiving documentation forms. Statistical analysis of the data and the creation of the final statistical report on the study will also be carried out by the responsible professional subcontractor for statistical analyses. The consistency of reported AE data will be ensured by reconciling the project database with the Servier drug safety database. Discrepancies will be resolved by mutual agreement between both parties (Servier and professional subcontractor for statistical analyses).

Statistical analysis

Due to the non-interventional nature of this study, statistical analysis will be carried out in descriptive and exploratory forms. All parameters will be analysed using descriptive statistics. For each parameter, the following will be specified: number of patients, mean value, standard error, minimum and maximum values, or proportion of each category. All composite endpoints will be listed and presented in visual form as graphs and in tables of parameters and their frequencies. For categorical variables, absolute values and rates in per cents be calculated. The calculations of relative rates will include only patients in whom values of the corresponding variables will be available.

All reports of adverse drug reactions (ARDs), adverse events (AEs), serious ADR/AE, and special situations will be encoded, and the results will be listed and classified according to the System-Organ-Classes (SOCs).

Accepted level of significance

In all tests, a significance level of 0.05 will be used, and 2-sided statistical tests will be carried out.

Report preparation

The preparation of the final report on the study will begin after the completion of the statistical analysis. The publication of the main results is planned within 12 months after the end of the study.

5 Ethical considerations

The study will be carried out in accordance with the principles of the Helsinki Declaration, according to the version revised in Brazil in 2013. The protocol must be reviewed and approved by an independent ethics committee after it is submitted by the coordinator or sponsor in accordance with local regulatory requirements, especially on the matters relating to data protection. Patients will be informed about the conditions for participation in the study, and they will have to provide written consent to participate in the study. The doctor must confirm in the Case report form (CRF) that the informed consent has been obtained, and he/she must keep one original of the signed informed consent form in the patient's file. "Informed consent" also means an individual discussion of procedures, that will be conducted as a part of the study, with the patient.

5.1 Patient data privacy

Investigators should maintain confidentiality of information about patients included in this study. Confidential data should contain enough information to contact the patient in case of emergency, or if further monitoring is required. Patient's right to privacy is of utmost importance. To protect the data confidentiality and preserve patient anonymity, patient's identity will be encoded in the study documentation. Patients can be identified using a unique number, age and gender, which will be recorded in the CRF. To reveal the patient's identity, all investigators will keep a confidential list for patient identification containing the names and addresses of the patients, as well as their assigned numbers. Thus, only investigator will be able to decode the identity of a patient.

6 Appendices

Appendix 1. Cardiovascular risk assessment. Classification of angina severity according to the Canadian Cardiovascular Society (15).

Functional class	Signs
I	«Latent» angina. Angina with only strenuous exertion.
II	Angina with ordinary activity: brisk walking or climbing hill or more than one flight of ordinary stairs, after meals, or under emotional stresses.
III	Angina markedly limits physical activity. Angina with low efforts: walking at a normal pace for less than 500 m, climbing 1-2 flights of stairs. Angina sometimes occurs at rest.
IV	Inability to carry on any, even minimal physical activity without angina. Anginal attacks occur at rest. A history of myocardial infarction or heart failure is common.

Appendix 2. Classification of blood pressure, and definitions of hypertension grade (2).

BP categories	SBP, mm Hg		DBP, mm Hg
Optimal	<120	and	<80
Normal	120–129	and/or	80–84
High normal	130–139	and/or	85–89
Grade 1	140–159	and/or	90–99
Grade 2	160–179	and/or	100–109
Grade 3	≥180	and/or	≥110
Isolated systolic hypertension ¹	≥140	and	<90

¹ Isolated systolic hypertension (ISH) should be classified into grades 1, 2, and 3 according to the SBP level.

Appendix 3. The New York Heart Association (NYHA) functional classification of heart failure (15).

Functional class	Patient Symptoms
I	No limitation of physical activity. Ordinary physical activity does not cause undue fatigue, palpitation, dyspnea (shortness of breath).
II	Slight limitation of physical activity. Comfortable at rest. Ordinary physical activity results in fatigue, palpitation, dyspnea (shortness of breath).
III	Marked limitation of physical activity. Comfortable at rest. Less than ordinary activity causes fatigue, palpitation, or dyspnea.
IV	Unable to carry on any physical activity without discomfort. Symptoms of heart failure at rest. If any physical activity is undertaken, discomfort increases.

Appendix 4. The (Modified) eight-item Morisky Medication Adherence Scale.

Patient Name:

Morisky Medication Adherence Scale (MMAS)

Please answer each question based on your personal experience with your medications. Note that there is not right or wrong answer. (Please circle your answer below)

1. Do you sometimes forget to take your medications?	NO	YES
2. People sometimes miss taking their medications for reasons other than forgetting. Thinking over the past two weeks, were there any days when you did not take your medications?	NO	YES
3. Have you ever cut back or stopped taking your medications without telling your doctor, because you felt worse when you took it?	NO	YES
4. When you travel or leave home, do you sometimes forget to bring along your medications?	NO	YES
5. Did you take your medications yesterday?	NO	YES
6. When you feel like your health condition is under control, do you sometimes stop taking your medications?	NO	YES
7. Taking medications every day is a real inconvenience for some people. Do you ever feel hassled about sticking to your treatment plan?	NO	YES
8. How often do you have difficulty remembering to take all your medications?	Never/rarely Once in a while Sometimes Usually All the time	4 3 2 1 0

Each “Never” response is rated as 1, except for item 5, in which “Yes” response is rated as 1, and other responses are rated as 0. Total scores range from 0 to 8, with scores of 8 reflecting high adherence, 7 or 6 reflecting medium adherence, and <6 reflecting low adherence.

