- To describe a proportion of patients who achieved resting HR less than 60 bpm at week 12 of prospective observation.
- To estimate association between the resting HR and achievement of target level of BP at week 12 of prospective observation.
- To describe adherence to the treatment with bisoprolol / perindopril in hypertensive patients with previous MI during the prospective observational period of 12 weeks.
- To describe the tolerability of treatment with bisoprolol / perindopril in hypertensive patients with previous MI during 12 week prospective observation.

Outcome measures

Primary outcome measure:

- Change in the mean systolic and diastolic BP levels at week 12 of prospective observation compared to baseline among patients included in the study.

Secondary outcome measures:

- Change in mean systolic and diastolic BP levels at week 4 of prospective observation compared with baseline.
- Change in number of angina attacks per week at week 4 of prospective observation compared with baseline.
- Change in number of angina attacks per week at week 12 of prospective observation compared with baseline.
- Proportion of patients who were taking lipid lowering therapy (LLT) at week 12 of prospective observation.
- Proportion of patients receiving LLT who achieved target levels of LDL C at week 12 of prospective observation.
- Proportion of patients who achieved SBP \leq 140 mm Hg and DBP \leq 90 mm Hg at week 4 of prospective observation.
- Proportion of patients who achieved SBP \leq 140 mm Hg and DBP \leq 90 mm Hg at week 12 of prospective observation.
- Proportion of patients younger than 65 who achieved SBP \leq 130 mm Hg and DBP \leq 80 mm Hg at week 4 of prospective observation .
- Proportion of patients younger than 65 who achieved SBP \leq 130 mm Hg and DBP \leq 80 mm Hg at week 12 of prospective observation.
- Proportion of patients older than 65 years who achieved SBP \leq 140 mm Hg and DBP \leq 90 mm Hg at week 4 of prospective observation.

- Proportion of patients older than 65 years who achieved SBP≤140 mm Hg and DBP ≤90 mm Hg at week 12 of prospective observation .
- Changes in the mean heart rate (HR) at week 4 of prospective observation compared with baseline.
- Changes in the mean heart rate (HR) at week 12 of prospective observation compared with baseline.
- Proportion of patients who achieved target level of resting HR (55-60 bpm) at week 4 of prospective observation.

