- Proportion of patients who achieved target level of resting HR (55-60 bpm) at week 12 of prospective observation.
- Correlation between the resting HR values stratified by groups and achievement of BP targets at week 12 of prospective observation .
- Proportions of patients with high, medium or low adherence to the treatment with SPC of bisoprolol/perindopril, assessed by MMAS-8 self-reporting questionnaire at week 4 of prospective observation.
- Proportions of patients with high, medium or low adherence to the treatment with SPC of bisoprolol/perindopril, assessed by MMAS-8 self-reporting questionnaire at week 12 of prospective observation.
- Incidence rate of adverse events/ adverse drug reactions and special situations during 12 week observational period of the study.

2 Methods and documentation

Study design and definitions

This is a multi-centre, observational, incomparative, ambispective study, which will retrospectively and prospectively collect clinical and socio-demographic data from medical records of patients with HTN and previous MI initiated with bisoprolol/perindopril SPC in real clinical settings.

Baseline data will be collected retrospectively from medical records of patients with HTN and a history of MI. Baseline data are defined as clinical parameters of interest available in medical records at the nearest date before or at the date of the initiation of SPC with Bisoprolol/ Perindopril.

To be included in the study for further prospective observation a patient should have been administered bisoprolol/ perindopril SPC within first three months before the Index Date. (*Fig.1*).

The Index date is a date when a decision to include a patient in the study for further 12 week prospective observation made by a treating physician after evaluation of recorded data to confirm patient's eligibility for the study.

Therefore, criteria for non-inclusion or inclusion of patients in the study are to be retrospectively evaluated by the treating physician using recorded clinical data available from medical records. Once a treating physician makes decision to include a patient in the study and, in particular, on the prospective observation for 3 months, a visit 0 (inclusion visit) to the clinic for obtaining signed patient's consent to participate in the study should be appointed and made within 1 month from the Index Date.

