2.7.2 Study schedule

According to the design of multicentre, non-intervention, open-label, incomparative, ambispective study in patients with HTN and CAD treated with a bisoprolol/perindopril SPC, three visits will be enough to include patients, evaluate the treatment effectiveness and safety, as well as to adjust the dose of the study drug* (3,8).

The following visits are scheduled:

1. Screening period: will be retrospectively performed to ensure each patient fulfills inclusion/non-inclusion criteria
2. Inclusion visit (V0): month 0;
3. Follow-up visit (V1): at 1 month after the V0 visit;
4. Final visit (V2): at month 3 after the visit V0 or in case of perindopril/ bisoprolol SPC treatment withdrawal.

* *In renal impairment, it is necessary to adjust the dose depending on the degree of impaired renal function (creatinine clearance)*

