- Current use of other cardiovascular drugs with doses for calcium channel blockers, diuretics, nitrates and statins;
- Baseline assessment of adherence to bisoprolol/perindopril SPC done by patient-reported 8 item Morisky Medication Adherence Scale;
- Adverse events/drug reactions/special situations.

2.7.4.2. Data collection at the follow-up visit (V1):

- Physical examination and vital signs;
- Current status of taking bisoprolol/perindopril SPC and a dose regimen;
- Number of weekly angina attacks;
- Current symptoms and the use of short-acting nitrates;
- Current use of antianginal agents;
- Adherence to bisoprolol/perindopril SPC assessed by patient-reported 8 items Morisky Medication Adherence Scale;
- Current use of other cardiovascular drugs with doses for calcium channel blockers, diuretics, nitrates and statins;
- Adverse events/drug reactions/special situations;

2.7.4.3. Data collection at the final visit (V2):

- Physical examination and vital signs;
- Current status of taking bisoprolol+perindopril SPC and a dose regimen;
- Number of weekly angina attacks ;
- Current symptoms and the use of short-acting nitrates;
- Current use of antianginal agents;
- Current use of other cardiovascular drugs with doses for calcium channel blockers, diuretics, nitrates and statins;

- Adherence to bisoprolol/perindopril SPC assessed by patient-reported 8 items Morisky Medication Adherence Scale;
- Adverse events/drug reactions/special situations;

[figure not shown]

Figure 1. The scheme of the PRIDE study.

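### The adherence outcomes are labelled as adherence to the bisoprolol/perindopril single pill, but the MMAS-8 form asks about all of the patient's medications

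*Combined protocol and SAP*

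**What the plan says.** The secondary objective in section 1 is specific to the SPC: "To describe adherence to the treatment with bisoprolol / perindopril in hypertensive patients with previous MI during the prospective observational period of 12 weeks". The outcome follows it: "Proportions of patients with high, medium or low adherence to the treatment with SPC of bisoprolol/perindopril, assessed by MMAS-8 self-reporting questionnaire at week 12", with a matching outcome at week 4. In section 2.7.4 the V1 and V2 lists repeat the label: "Adherence to bisoprolol/perindopril SPC assessed by patient-reported 8 items Morisky Medication Adherence Scale". The V0 list does the same for the baseline assessment.

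The form itself, in Appendix 4, is general. Its instruction is "Please answer each question based on your personal experience with your medications". Items 1 to 6 refer to the patient's medications, for example item 5, "Did you take your medications yesterday". Item 7 is worded differently but is just as broad: "Do you ever feel hassled about sticking to your treatment plan". Item 8 asks about remembering all medications. A score of 8 is high adherence, 6 or 7 is medium, and below 6 is low.

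Three other provisions matter:

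- Section 2 (Concomitant drugs) permits any other treatment that the physician thinks necessary and that is not contraindicated. The visit lists track antianginals, calcium channel blockers, diuretics, nitrates and statins.
- Section 2.7.2 sets the final visit at month 3 "or in case of perindopril/ bisoprolol SPC treatment withdrawal", and that visit includes the MMAS-8.
- Section 4 (Statistical analysis) calculates percentages over all patients with an available value. Table 1 records current SPC use and reasons for stopping at V0, V1 and V2, but no rule links that record to the MMAS-8 category.

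**The concern.** The label and the questionnaire describe different things. Patients with hypertension, angina and a previous infarction will often take several other drugs, so their answers need not be about the SPC. Nothing in the protocol tells patients or physicians to answer for the SPC alone.

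The error can run either way. Lapses on another drug can lower the category of a patient who never misses the SPC. Good habits with the remaining drugs can give a high category to a patient who no longer takes the SPC at all.

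At stake is what the study may say about adherence. The Introduction cites a 24% gain in adherence with single pills over free combinations, and 66.5% in an earlier study of this SPC. A percentage labelled as adherence to the SPC invites comparison with those figures, which the form as worded cannot support.

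**Working it through.** **1. The plan's own figure.** Appendix 4 gives a score range of 0 to 8. Items 1 to 7 are yes/no and carry one point each for the adherent answer (No for items 1-4, 6 and 7; Yes for item 5). Item 8 earns one point for the never/rarely answer and none otherwise. The minimum is 0 and the maximum is 7 + 1 = 8, so the stated range is reproduced. Two readings are needed for this. The scoring note's 'Never' is taken as 'No' for the yes/no items. Item 8 is scored 0 or 1, because adding its printed codes of 4 to 0 would give a maximum of 7 + 4 = 11.

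**2. Scores for specific patients.** Score = 8 minus the number of items on which the point is lost.

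| Patient | Points lost | Score | Category |
|---|---|---|---|
| SPC stopped with the doctor's knowledge, all other drugs taken | none | 8 | high |
| SPC stopped on feeling worse, doctor not told | item 3 | 7 | medium |
| Same, also counting missed days in the last two weeks | items 2, 3 | 6 | medium |
| SPC taken perfectly, another drug forgotten | items 1, 8 | 6 | medium |
| Same, with a missed day in the last two weeks | items 1, 2, 8 | 5 | low |

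The first row escapes item 3 because that item asks "Have you ever cut back or stopped taking your medications without telling your doctor", and here the doctor knows.

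**3. Whether the first patient reaches the result.** Withdrawal of the SPC triggers V2, V2 includes the form, and the denominator rule keeps every available value. No provision removes or reclassifies this patient, so the score of 8 counts towards high adherence to the SPC.

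**4. Size of the false high share.** Let w be the share of patients with an MMAS-8 value who are off the SPC, and q the share of those who score 8. The false high share is w × q. The documents give neither input, so both are assumed:

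- w = 5%, q = 0.5: 2.5 points
- w = 5%, q = 1: 5 points (25 of 500 patients)
- w = 10%, q = 0.5: 5 points (25 of 500)
- w = 10%, q = 1: 10 points (50 of 500)

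Worked example at the upper end: assume 60% are high among patients still on the SPC, with w = 10% and q = 1. The reported high share is 0.60 × 0.90 + 0.10 = 0.64. Without the patients who stopped in the numerator, it is 0.60 × 0.90 = 0.54.

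**5. The opposite error.** The documents give no rate of lapses on other drugs, so no size is put on the downward misclassification. It would partly offset the upward one, and the net direction is unknown.

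**The case against.** The SPC is one of the patient's medications, so missed SPC doses also lower the score and the scale is not blind to the SPC. General wording is the form in which the scale is set out in Appendix 4, and the protocol cites a predictive-validity study for the instrument. SPC use and reasons for stopping are recorded at every visit, and section 4 says all parameters will be summarised, so persistence should be tabulated anyway. The outcome is secondary and descriptive, in a study without a comparator. All of this stands. It limits the weight of the point, but it does not reconcile the label with the form or say how patients off the SPC are classified.

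A reader might infer more than the documents support:

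- *That other drugs decide the score, so the objective goes unanswered.* Other drugs enter the score and can tip it, but SPC lapses count as well.
- *That anyone who stops the SPC is counted as highly adherent.* A patient who stopped on feeling worse without telling the doctor, and who answers truthfully, loses item 3 and lands in medium. A false high arises mainly from stops the doctor knows about.
- *That the score reflects lifetime history because item 3 asks about 'ever'.* A past undisclosed stop on any drug could rule out a score of 8. But item 2 covers two weeks, item 5 covers yesterday, and items 1, 4 and 6 are in the present tense. No change from V0 is planned for this outcome.
- *That the downward error can be found by multiplying a separate risk for each drug.* This needs independence between drugs. Forgetting is plausibly a habit of the patient, and the documents give no rates.

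**Conclusion.** The point holds. As written, the plan would report a general medication-adherence score under an SPC-specific label, and a patient no longer taking the SPC can appear as highly adherent to it. Under assumed discontinuation of 5-10%, with half to all of those patients scoring 8, the false high share is 2.5-10 percentage points. That range rests on the assumptions, not on any figure in the documents, and it leaves out the opposite error from lapses on other drugs.

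The label problem affects both time points. The route through a final visit held on withdrawal bears chiefly on week 12; at week 4 it needs a patient who is off the SPC but still completes the V1 form. The consequence is confined to how the adherence proportions may be interpreted. The primary outcome and the sample size do not change.

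**What to change.** 1. Retitle the week 4 and week 12 outcomes, and the wording in the V0, V1 and V2 lists, as adherence to all current medications by MMAS-8. Leave the scale as it is: rewording the items for the SPC would trade comparability and the cited validity evidence for specificity.
2. Report SPC persistence at V1 and V2, with reasons for stopping, from the Table 1 row on current SPC use. Make this the SPC-specific measure.
3. Wherever adherence is presented in relation to the SPC, show patients off it at that visit as a separate off-SPC category, kept in the denominator. Do not place them in high, medium or low adherence to the SPC. Do not score them as non-adherent either: a stop directed by the physician is not a failure of adherence, and that label would create a new misclassification.

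The cost is wording and one added tabulation; no new data or visits are needed. The downside is that the MMAS-8 result will no longer support a statement about adherence to the SPC specifically.

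### The MMAS-8 scoring note in Appendix 4 does not fit the printed form: followed literally, the total cannot exceed 2, yet the plan states a range of 0 to 8

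*Combined protocol and SAP*

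**What the plan says.** Appendix 4 prints eight questions. Items 1 to 7 offer two answers each, *No* and *Yes*. Item 8 ("How often do you have difficulty remembering to take all your medications") offers five, "Never/rarely Once in a while Sometimes Usually All the time", with the numbers 4, 3, 2, 1, 0 beside them.

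The scoring note under the form says "Each “Never” response is rated as 1, except for item 5". On item 5 ("Did you take your medications yesterday") a *Yes* "response is rated as 1, and other responses are rated as 0. Total scores range from 0 to 8". The bands follow, "with scores of 8 reflecting high adherence, 7 or 6 reflecting medium adherence, and <6 reflecting low adherence".

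The score serves a secondary objective in Section 1, "To describe adherence to the treatment with bisoprolol / perindopril in hypertensive patients with previous MI during the prospective observational period of 12 weeks". It also defines two secondary outcome measures: the split into high, medium and low adherence at week 4, and the same at week 12 ("Proportions of patients with high, medium or low adherence to the treatment with SPC of bisoprolol/perindopril, assessed by MMAS-8 self-reporting questionnaire at week 12"). Table 1 in Section 2.7.4 has the scale completed at V0, V1 and V2. Section 4 assigns data entry and statistical analysis to a subcontractor and gives no scoring rule of its own.

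**The concern.** The note and the form do not describe the same questionnaire. The note awards the point to an answer that six of the items do not offer, and gives zero to everything else. For item 8 it implies one point or none, while the form shows a five-step numbering that the note never mentions.

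Appendix 4 is the only place in the documents where scoring is defined, and the person applying it works for an outside subcontractor. Anyone who follows the text exactly gets a wrong result. Anyone who departs from it has to decide how, and the reported adherence categories depend on that decision.

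**Working it through.** **Inputs, all from Appendix 4.** Items 1-4, 6 and 7 (six items): *No* or *Yes*. Item 5: *No* or *Yes*, with *Yes* = 1. Item 8: five options numbered 4, 3, 2, 1, 0. Stated total: 0 to 8. Bands: 8 high; 6 or 7 medium; below 6 low. There are 2^7 × 5 = 640 possible answer patterns, and all were scored under each reading.

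**Maximum total under each reading** (six items + item 5 + item 8; the minimum is 0 in every case):

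| Reading | Maximum | Consequence |
|---|---|---|
| A. Note taken literally, *Never/rarely* counted as *Never* | 0 + 1 + 1 = 2 | Everyone is low |
| A'. As A, but *Never/rarely* not counted as *Never* | 0 + 1 + 0 = 1 | Everyone is low |
| B. Six items literal, item 8 numbers added | 0 + 1 + 4 = 5 | Everyone is low |
| C. *No* = 1, item 8 scored 1/0 | 6 + 1 + 1 = 8 | Every total has a band |
| D. *No* = 1, item 8 numbers added | 6 + 1 + 4 = 11 | Totals 9, 10 and 11 have no band |
| E. *No* = 1, item 8 number divided by 4 (an assumption; not in the documents) | 6 + 1 + 4/4 = 8 | Some fractional totals have no band |

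The stated range of 0 to 8 is not reproduced by the note as written (A or A'). C reproduces it in whole numbers that all fall in a band. E reaches the same range only with fractional totals.

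**What reading D does to the categories.** Let k be the number of adherent answers on items 1-7 and n the item 8 number. D gives k + n. C gives k + 1 if n = 4, and k otherwise.

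- A total of 8 under D, labelled high, arises only from (k, n) = (4,4), (5,3), (6,2) and (7,1). Under C these score 5, 5, 6 and 7: low, low, medium, medium. None is high.
- Totals of 9 to 11 under D arise only from (5,4), (6,3), (7,2), (6,4), (7,3) and (7,4). Under C these score 6, 6, 7, 7, 7 and 8: five medium and one high. The patient with the best possible answers, (7,4), totals 11 and has no category.

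**Reading E.** With k = 6 or 7 and n = 1, 2 or 3, the totals are 6.25, 6.5, 6.75, 7.25, 7.5 and 7.75, none of which is 6 or 7. If medium is defined as 6 to below 8, all 640 patterns receive the same category as under C.

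These results hold for any distribution of answers. The documents give no such distribution, so the number of patients affected cannot be estimated, and pattern counts are not patient counts.

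**The case against.** The strongest reply is that the note resolves itself. It has a 1/0 rule, a total of 0 to 8, whole-number bands, and item 5 singled out because *Yes* earns the point there, which implies that the negative answer earns it elsewhere. Only reading C fits all of this, so *Never* is probably a slip for *No*. Readings A and D each contradict something else in the note, and nothing shows that the subcontractor would use either. The 4-0 numbers conflict with the note only if they are points, and the documents do not say that they are. The outcomes are descriptive, in a study that declares itself exploratory.

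Most of this stands, and it limits the severity. The intended score can be inferred, and the readings above show what could follow; they do not predict what will happen. The inference still requires the scorer to override a written word for six items and to set aside numbers printed on the form.

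The reference list includes a paper on a medication adherence measure, but Appendix 4 does not cite it as the scoring source and calls its own version modified. The text was read from a PDF, so the position of the 4-0 numbers needs checking on the original form. The mismatch between *Never* and *No*/*Yes* does not depend on layout.

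**Conclusion.** The scoring rule is wrong as written. Followed exactly, it gives at most 2 points (1 on the strictest reading), cannot produce the stated total of 8, and makes the proportions with medium and high adherence 0% at both week 4 and week 12. Adding the printed item 8 numbers instead leaves the most adherent patients without a category and labels low or medium patients as high.

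The error should be fixed but is not grave. The intended score (reading C) can be recovered from the note, the outcomes are two descriptive secondary measures, patients' answers are unaffected, and the primary blood pressure outcome is not touched. The literal result rests only on the legible answer options and the text of the note. The result for added numbers also assumes that the 4-0 numbers stand on the original form as they appear in the extracted text.

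**What to change.** Before scoring, replace the note in Appendix 4 with:

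- Items 1-4, 6 and 7: *No* = 1, *Yes* = 0.
- Item 5: *Yes* = 1, *No* = 0.
- Item 8: *Never/rarely* = 1, any other answer = 0. The numbers 4 to 0 beside the options do not enter the total (wording to be confirmed against the original form).
- Total 0 to 8: 8 high, 6 or 7 medium, below 6 low.

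If the sponsor instead intends item 8 as its number divided by 4, the note should say so and define medium as 6 to below 8. The categories are then the same.

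The cost is one corrected note, also sent to the subcontractor as a scoring instruction. No question or visit changes, and forms already printed can stay in use. The documents do not say whether item answers or only totals are entered; if only totals, they would have to be recalculated from the completed paper forms.
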